#### 14.1.6.7 Extent of Exposure

Extent of exposure for a subject is defined as number of cycles in which the subject receives the study medication infusion. Summary statistics will be provided on Extent of Exposure for treated participant study population.

### **14.2 Populations for Analyses**

- Enrolled participants: All participants who signed an informed consent form and were registered into the study. This is the dataset for disposition.
- Treated participants: All participants who received at least one dose of study drug. This is the dataset for baseline demographics, efficacy, and safety evaluation.
- Response-Evaluable participants: All treated participants with measurable disease at a baseline tumor assessment.
- Biomarker participants: All treated participants with available biomarker data.
- NANO participants: All treated participants with available NANO data (Cohorts 1c, 1d, and 2)

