### **5.2.5 Radiation Therapy**

The following applies to patients on cohort 2:

What: On-study Radiation Therapy will be administered according to established, institutional standard-of-care guidelines utilizing one of the following techniques for reirradiation and best clinician judgment:

- fractionated intensity-modulated radiation therapy (IMRT)
- 3-dimensional conformal radiation therapy (3D-CRT)
- or proton beam radiation therapy
- stereotactic radiosurgery
- or fractionated stereotactic radiotherapy

When: To occur prior to initiation of Cycle 1 of Nivolumab + Ipilimumab. Day 1 Cycle 1 of study immunotherapy will be no sooner than 1 week from the completion of XRT, and no later than 12 weeks after completion of XRT.

Where: Participants are permitted to receive re-irradiation on study at the following locations:  
a. the Radiation Oncology Department of the participating institution;  
b. an IRB-approved satellite site of the participating institution;

CONFIDENTIAL

This document is confidential. Do not disclose or use except as authorized.

- c. any NRG Oncology-approved site;
- d. or at another location, with **prior documented approval from the study's Overall PI.**

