## **5.7 Pre-Treatment Criteria**

Cohort 1: Nivolumab dosing will continue every 2 weeks unless criteria for dose delay (Section 6.1) or study discontinuation criteria (Section 6.4) are met. In the event of a dose delay, dosing will be resumed when criteria to resume treatment (Section 6.3) are met.

**NOTE:** Participants who have received active study therapy for  $>/=$  6 months will be allowed the option to adjust their Nivolumab dosing schedule from 240 mg once every 2 weeks (-2/+5 days) to 480 mg once every 4 weeks (+/- 1 week).

Cohort 2: Treatment with study therapy [External Beam RT followed by 4 cycles of Nivolumab + Ipilimumab (dosing every 3 weeks), followed by Nivolumab monotherapy (dosing every 4 weeks)] unless criteria for dose delay (Section 6.1) or study discontinuation criteria (Section 6.4) are met. In the event of a dose delay, dosing will be resumed when criteria to resume treatment (Section 6.3) are met.

CONFIDENTIAL

This document is confidential. Do not disclose or use except as authorized.

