## 5.8 Study Agents

Study drugs include both Non-investigational (NIMP) and Investigational Medicinal Products (IMP) and can consist of the following:

- All products, active or placebo, being tested or used as a comparator in a clinical trial.
- Study required premedication, and
- Other drugs administered as part of the study that are critical to claims of efficacy (e.g., background therapy, rescue medications)

Diagnostic agents: (such as glucose for glucose challenge) given as part of the protocol requirements must also be included in the dosing data collection.

An investigational product, also known as investigational medicinal product in some regions, is defined a pharmaceutical form of an active substance or placebo being tested or used as a reference in a clinical study, including products already with a marketing authorization but used or assembled (formulated or packaged) differently than the authorized form, or used for an unauthorized indication, or when used to gain further information about the authorized form.

The investigational product should be stored in a secure area according to local regulations. It is the responsibility of the investigator to ensure that investigational product is only dispensed to study subjects. The investigational product must be dispensed only from official study sites by authorized personnel according to local regulations.

In this protocol, investigational products are: BMS-936558 (nivolumab) and BMS-734016 (ipilimumab).

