#### 7.2.6 Attribution of the AE:

The causal relationship will be made for each of the agents of study therapy: nivolumab, ipilimumab (when applicable), and radiation (when applicable). Attribution is determined by an appropriately trained and delegated clinician and should be used to assess all adverse events (AE). The causal relationship can be one of the following:

- Definite – The AE is *clearly related* to the study treatment.
- Probable – The AE is *likely related* to the study treatment.
- Possible – The AE *may be related* to the study treatment.
- Unlikely – The AE is *doubtfully related* to the study treatment.
- Unrelated – The AE is *clearly NOT related* to the study treatment.

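### Cohort 2 efficacy set requires a drug infusion, so participants who fail between on-study radiation and Cycle 1 leave the PFS-6 denominator and the estimate is biased upward

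*Combined protocol and SAP*

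**What the plan says.** Section 14.2 sets membership by drug exposure: "Treated participants: All participants who received at least one dose of study drug. This is the dataset for baseline demographics, efficacy, and safety evaluation". The wider enrolled set has a different use: "All participants who signed an informed consent form and were registered into the study. This is the dataset for disposition".

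Section 5.8 ties study drug to the two antibodies: "In this protocol, investigational products are: BMS-936558 (nivolumab) and BMS-734016 (ipilimumab". The opening of Section 7 likewise takes the first dose of study treatment to be the first infusion of either antibody. Radiation does not bring a participant into the efficacy set.

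Elsewhere, radiation is part of Cohort 2 study therapy. Section 5.7 has "Treatment with study therapy [External Beam RT followed by 4 cycles of Nivolumab + Ipilimumab", and Section 7.2.6 asks for attribution "for each of the agents of study therapy: nivolumab, ipilimumab (when applicable), and radiation (when applicable". Section 5.2.5 calls the radiation on-study and places Cycle 1 Day 1 "no sooner than 1 week from the completion of XRT, and no later than 12 weeks after completion of XRT". Section 4.1 requires registration before any protocol-specific therapy. Section 3.1.9 also lets Cohort 2 participants enrol while receiving radiotherapy or after completing it.

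Sections 11.2, 14.1.2.1 and 14.1.6.1 define PFS-6 as a proportion of the analysis population, counted from initiation of study therapy.

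**The concern.** The primary objective (1.2.1) for Cohort 2 concerns the sequence of radiation and then both antibodies. A participant who starts that sequence and progresses, deteriorates or dies before Cycle 1 is a failure of the regimen under test. Section 14.2 nevertheless leaves that participant in the disposition data only. Nothing in Section 14 restores such participants or plans a sensitivity analysis that includes them.

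Removing failures from a denominator can only raise a proportion. The cohort has about 25 participants and is judged against a historical rate, so a few early losses visibly move the headline figure. Section 14 says that no separate SAP will be issued, so the protocol text is where this has to be settled.

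**Working it through.** **Inputs.** From 14.1.4: n = 25 per cohort, null 26%, alternative 51%, success if at least 10 are progression-free at six months, stated exact alpha 0.089 and power 90%. From 14.1.5.1: continue if at least 3 of the first 10 evaluable are progression-free; stated stopping chances 0.5 and 0.048. Assumed, because the documents give no figure: the number k, or share q, of participants who start on-study therapy and fail before the first infusion.

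**Step 1: reproduce the plan.** Exact binomial:
- P(X ≥ 10 | 25, 0.26) = 0.0893, which matches 0.089.
- P(X ≥ 10 | 25, 0.51) = 0.904, which matches 90%.
- P(X ≤ 2 | 10, p) = 0.496 at 26% and 0.048 at 51%, which match 0.5 and 0.048.

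The stated 0.089 is the single-stage figure; with the interim stop included it is 0.082.

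**Step 2: 25 enrolled, no replacement.** Reported PFS-6 with 10 progression-free is 10/(25 − k). A true regimen rate of 26% appears as 0.26 × 25/(25 − k).

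| k lost before infusion | 10 progression-free reported as | true 26% appears as |
|---|---|---|
| 0 | 40.0% | 26.0% |
| 1 | 41.7% | 27.1% |
| 2 | 43.5% | 28.3% |
| 3 | 45.5% | 29.5% |
| 5 | 50.0% | 32.5% |

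The numerator counts participants who are progression-free, so dropping failures leaves it unchanged. The final rule is a count of at least 10, and dropping failures cannot add to it. Alpha stays at 0.089.

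**Step 3: losses replaced until 25 are infused.** If the true rate among all who start is 26% and a share q fails before infusion, the rate among the infused is 0.26/(1 − q). If the interim 10 are also infused participants, the same rate applies there.

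| q (assumed) | rate among infused | P(X ≥ 10 of 25) | interim stop, P(X ≤ 2 of 10) |
|---|---|---|---|
| 0 | 26.0% | 0.089 | 0.496 |
| 5% | 27.4% | 0.119 | 0.456 |
| 10% | 28.9% | 0.157 | 0.413 |
| 20% | 32.5% | 0.273 | 0.319 |

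**Step 4: which scenario do the documents describe?** The Trial Summary speaks of approximately 25 enrolled per cohort. Section 14.1.4 says 25 patients per cohort without saying registered or infused. Replacement is stated only for the safety lead-in (5.2.2). Section 14.1.5.1 does not define evaluable for PFS-6.

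**Step 5: when does the clock start?** Sections 5.7 and 7.2.6 make radiation the start of study therapy. Section 5.2.2 treats the first 42 days of study therapy as six weeks from Day 1 of drug, and calendar footnote x in Section 10 places the baseline scan close to study therapy initiation while tying it to the first dose. Both point to the first infusion. For the secondary time-to-event PFS, 14.1.2.2 counts from initiation of study therapy and 14.1.6.1 from allocation. Time zero for Cohort 2 is therefore not settled.

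**The case against.** The strongest reply is that set and clock can be read consistently. If study therapy begins at the first infusion, as 5.2.2, footnote x and the baseline rule in 11.1.2 suggest, then baseline scan, time zero and analysis set all coincide, and PFS-6 is a coherent measure from Cycle 1. A reader might infer that the radiation-to-drug gap is guaranteed event-free time credited to the regimen. The documents do not establish that, because it needs a clock that starts at radiation. Even so, a PFS-6 from first infusion describes only those who reached infusion, which is narrower than the regimen named in the objective.

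Second, not everyone is exposed to the bias. Participants who enrol after completing radiation (3.1.9) have no on-study gap in which to be lost. They were selected before entry on having come through it, and no change of analysis set can undo that. How many enter by each route is unknown.

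Third, part of the reporting already exists. The enrolled set is kept for disposition, 14.1.6.3 displays the reasons for discontinuation, and 4.1 records participants who receive no protocol therapy. None of this puts pre-infusion failures into PFS-6 or isolates losses between radiation and Cycle 1.

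Fourth, the Cohort 2 calendar shows no imaging in its radiation column. If the only baseline scan is the one near Cycle 1, radiographic progression in the gap has no reference scan. This is a practical limit on what can be counted; deaths and clear clinical deterioration do not depend on it.

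**Conclusion.** The concern stands for the estimate. As written, 14.2 removes from the Cohort 2 PFS-6 denominator any participant registered before or during radiation who fails before the first infusion. The direction is upward. The size depends on an unknown number: one to five losses among 25 enrolled would turn 40.0% into 41.7% to 50.0%.

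A reader might go further and infer that the test itself is anticonservative. The documents do not support that as a general conclusion. With 25 enrolled and no replacement the decision is unchanged and alpha remains 0.089. The values 0.119, 0.157 and 0.273 require both replacement up to 25 infused, which is not stated outside the lead-in, and assumed pre-infusion failure of 5%, 10% or 20%, for which the documents offer no anchor. They show what the unclear wording could permit.

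**What to change.** - In 14.1.2.1 and 14.2, state time zero for Cohort 2, and bring 5.2.2, 5.7, 7.2.6, 14.1.2.2, 14.1.6.1 and calendar footnote x into line with it.
- In 14.2, define the Cohort 2 efficacy set as all registered participants who start on-study radiation or study drug. Count progression, deterioration or death before the first infusion as a PFS-6 failure.
- If the drug-treated set stays primary, prespecify that PFS-6 as a supportive result, and report the number lost between radiation and Cycle 1 with reasons.
- In 14.1.4 and 14.1.5.1, say whether the 25 per cohort and the interim 10 evaluable are registered or infused participants.

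Cost: because Section 14 holds the only analysis plan, a change to the primary analysis needs a protocol amendment with IRB approval (Sections 14 and 13.1). The reported PFS-6 may be slightly lower. With 25 registered participants in the denominator, the stated alpha of 0.089 and power of 0.904 apply to the regimen as a whole. Selection before entry among those who enrol after radiation remains and should be acknowledged when results are reported.

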### **15. PUBLICATION PLAN**

This trial is intended for publication, even if terminated prematurely. Publication may include any or all of the following: posting of a synopsis online, abstract and/or presentation at a scientific conference, or publication of a full manuscript. The Principal Investigator and/or designee will work to submit a manuscript describing trial results within 12 months after the last data become available, which may take up to several months after the last participant visit in some cases such as vaccine trials. However, manuscript submission timelines may be extended.

Authorship credit should be based on 1) substantial contributions to conception and design, or acquisition of data, or analysis and interpretation of data; 2) drafting the article or revising it critically for important intellectual content; and 3) final approval of the version to be published. Authors must meet conditions 1, 2 and 3. Significant contributions to trial execution may also be taken into account to determine authorship, provided that contributions have also been made to all three of the preceding authorship criteria. Although publication planning may begin before conducting the trial, final decisions on authorship and the order of authors' names will be made based on participation and actual contributions to the trial and writing, as discussed above. The first author is responsible for defending the integrity of the data, method(s) of data analysis and the scientific content of the manuscript.

CONFIDENTIAL

This document is confidential. Do not disclose or use except as authorized.

## **APPENDIX B                    MANAGEMENT ALGORITHMS - NIVOLUMAB**

[figure not shown]
- These general guidelines constitute guidance to the Investigator and may be supplemented by discussions with the Overall PI. The guidance was designed for all immuno-oncology (I-O) agents and regimens, and – for the purpose of this trial – will be utilized for nivolumab.
- Where applicable the Approved Label should be used for guidance around dose modifications and discontinuation
- A general principle is that differential diagnoses should be diligently evaluated according to standard medical practice. Non-inflammatory etiologies should be considered and appropriately treated.
- Corticosteroids are a primary therapy for immuno-oncology drug-related adverse events. The oral equivalent of the recommended IV doses may be considered for ambulatory patients with low-grade toxicity. The lower bioavailability of oral corticosteroids should be taken into account when switching to the equivalent dose of oral corticosteroids.
- Consultation with a medical or surgical specialist, especially prior to an invasive diagnostic or therapeutic procedure, is recommended.
- The frequency and severity of the related adverse events covered by these algorithms will depend on the immuno-oncology agent or regimen being used.
- Investigators should refer to the most current version of the IB or Approved Label for current recommendations for management of a specific Adverse Event of interest.
- On the next 7 pages, find Nivolumab Management Algorithms for the following AEs:
  - GI AEs
  - Renal AEs
  - Pulmonary AEs
  - Hepatic AEs
  - Endocrinopathy
  - Skin AEs
  - Neurological AEs

CONFIDENTIAL

This document is confidential. Do not disclose or use except as authorized.

## GI Adverse Event Management Algorithm

Rule out non-inflammatory causes. If non-inflammatory cause is identified, treat accordingly and continue I-O therapy. Opiates/narcotics may mask symptoms of perforation. Infliximab should not be used in cases of perforation or sepsis.

[figure not shown]
Patients on IV steroids may be switched to an equivalent dose of oral corticosteroids (e.g. prednisone) at start of tapering or earlier, once sustained clinical improvement is observed. Lower bioavailability of oral corticosteroids should be taken into account when switching to the equivalent dose of oral corticosteroids.

CONFIDENTIAL

This document is confidential. Do not disclose or use except as authorized.

## Renal Adverse Event Management Algorithm

Rule out non-inflammatory causes. If non-inflammatory cause, treat accordingly and continue I-O therapy

[figure not shown]
Patients on IV steroids may be switched to an equivalent dose of oral corticosteroids (e.g. prednisone) at start of tapering or earlier, once sustained clinical improvement is observed. Lower bioavailability of oral corticosteroids should be taken into account when switching to the equivalent dose of oral corticosteroids.

CONFIDENTIAL

This document is confidential. Do not disclose or use except as authorized.

## Pulmonary Adverse Event Management Algorithm

Rule out non-inflammatory causes. If non-inflammatory cause, treat accordingly and continue I-O therapy. Evaluate with imaging and pulmonary consultation.

[figure not shown]
Patients on IV steroids may be switched to an equivalent dose of oral corticosteroids (e.g. prednisone) at start of tapering or earlier, once sustained clinical improvement is observed. Lower bioavailability of oral corticosteroids should be taken into account when switching to the equivalent dose of oral corticosteroids.

CONFIDENTIAL

This document is confidential. Do not disclose or use except as authorized.

## Hepatic Adverse Event Management Algorithm

Rule out non-inflammatory causes. If non-inflammatory cause, treat accordingly and continue I-O therapy. Consider imaging for obstruction.

Patients on IV steroids may be switched to an equivalent dose of oral corticosteroids (e.g. prednisone) at start of tapering or earlier, once sustained clinical improvement is observed. Lower bioavailability of oral corticosteroids should be taken into account when switching to the equivalent dose of oral corticosteroids.

\*I-O therapy may be delayed rather than discontinued if AST/ALT ≤ 8 x ULN or T.bili ≤ 5 x ULN.

[figure not shown]
\*\*The recommended starting dose for grade 4 hepatitis is 2 mg/kg/day methylprednisolone IV.

CONFIDENTIAL

This document is confidential. Do not disclose or use except as authorized.

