### **5.10 Criteria for Taking a Participant Off Protocol Therapy**

Duration of therapy will depend on individual response, evidence of disease progression and tolerance. In the absence of treatment delays due to adverse event(s), treatment may continue for indefinitely or until one of the following criteria applies:

- Confirmed radiological disease progression or investigator assessed clinical progression as described in Section 11.4;

CONFIDENTIAL

This document is confidential. Do not disclose or use except as authorized.

- Unacceptable adverse event/toxicity as specified in Section 6.4;
- Any clinical adverse event (AE), laboratory abnormality or intercurrent illness which, in the opinion of the investigator, indicates that continued participation in the study is not in the best interest of the participant;
- Participant demonstrates an inability or unwillingness to comply with the oral medication regimen and/or documentation requirements;
- Participant decides to withdraw from the protocol therapy;
- General or specific changes in the participant's condition render the participant unacceptable for further treatment in the judgment of the treating investigator
- Pregnancy;
- Loss of ability to freely provide consent through imprisonment or involuntarily incarceration for treatment of either a psychiatric or physical (eg, infectious disease) illness;
- Termination of the trial by the study's sponsor.

Participants will be removed from the protocol therapy when any of these criteria apply. The reason for removal from protocol therapy, and the date the participant was removed, must be documented in the subject's medical records and on the appropriate case report form (CRF). Alternative care options will be discussed with the participant.

All subjects who discontinue investigational product should comply with protocol specified follow-up procedures as outlined in Section 5.2. The only exception to this requirement is when a subject withdraws consent for all study procedures including post-treatment study follow-up or loses the ability to consent freely (i.e. is imprisoned or involuntarily incarcerated for the treatment of either a psychiatric or physical illness).

When a participant is removed from protocol therapy and/or is off of the study, the relevant Off-Treatment/Off-Study information will be updated in OnCore.

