### **6.1.1 Management Algorithms for Immuno-Oncology Agents**

Immuno-oncology (I-O) agents are associated with adverse events that can differ in severity and duration than adverse events caused by other therapeutic classes. Nivolumab and ipilimumab are considered immuno-oncology agents in this protocol.

Early recognition and management of adverse events associated with immuno-oncology agents may mitigate severe toxicity. Management algorithms have been developed to assist investigators in assessing and managing the following groups of adverse events:

• Gastrointestinal

• Renal

• Pulmonary

• Hepatic

	

• Endocrinopathies

• Skin

• Neurological

--	--

The algorithms recommended for utilization in this protocol are included in Appendix B (Nivolumab) and Appendix C (Ipilimumab).

For participants expected to require more than 4 weeks of corticosteroids or other immunosuppressants to manage an adverse event, consider recommendations provided in Appendix B (Nivolumab) and Appendix C (Ipilimumab). The guidance provided in these algorithms should not replace the Investigator's medical judgment but should complement it.

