#### **6.4 Discontinuation Criteria**

Treatment with combination nivolumab and ipilimumab must be permanently discontinued for the following:

- Any Grade  $\geq 2$  drug-related uveitis or eye pain or blurred vision that does not respond to topical therapy and does not improve to Grade 1 severity within the re-treatment period OR requires systemic treatment
- Any Grade  $\geq 3$  non-skin, drug-related adverse event lasting  $> 7$  days, with the following exceptions for drug-related laboratory abnormalities, uveitis, pneumonitis, bronchospasm, diarrhea, colitis, neurologic toxicity, hypersensitivity reactions, infusion reactions, and endocrinopathies:
  - Grade  $\geq 3$  drug-related uveitis, pneumonitis, bronchospasm, diarrhea, colitis, neurologic toxicity, hypersensitivity reaction, or infusion reaction of any duration requires discontinuation
  - Grade 3 drug-related endocrinopathies adequately controlled with only physiologic hormone replacement do not require discontinuation
  - Grade 3 drug-related laboratory abnormalities do not require treatment discontinuation except those noted below:
    - ◆ Grade  $\geq 3$  drug-related thrombocytopenia  $> 7$  days or associated with bleeding requires discontinuation
    - ◆ Any drug-related liver function test (LFT) abnormality that meets the following criteria requires discontinuation:
      - AST or ALT  $> 8 \times$  ULN
      - Total bilirubin  $> 5 \times$  ULN
      - Concurrent AST or ALT  $> 3 \times$  ULN and total bilirubin  $> 2 \times$  ULN
- Any Grade 4 drug-related adverse event or laboratory abnormality, except for the following events which do not require discontinuation:
  - Isolated Grade 4 amylase or lipase abnormalities that are not associated with symptoms or clinical manifestations of pancreatitis and decrease to  $<$  Grade 4 within 1 week of onset.
  - Isolated Grade 4 electrolyte imbalances/abnormalities that are not associated with clinical sequelae and are corrected with supplementation/appropriate management within 72 hours of their onset
  - Grade 4 lymphopenia or leukopenia

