## Hepatotoxicity Management Algorithm

[figure not shown]
\*Ipilimumab may be held/delayed rather than discontinued if AST/ALT  $\leq 8 \times$  ULN and Tbili  $\leq 5 \times$  ULN. Resume ipilimumab when AST/ALT/Tbili return to grade 2 and meet protocol specific retreatment criteria.

\*\*The recommended starting dose for grade 4 hepatitis is 2 mg/kg/day methylprednisolone IV.

\*\*\* MMF, mycophenolate mofetil

[figure not shown]
Patients on IV steroids may be switched to oral corticosteroid (e.g., prednisone) at an equivalent dose at start of tapering or earlier, once sustained clinical improvement is observed. Lower bioavailability of oral corticosteroids should be taken into account when switching to the equivalent dose of PO corticosteroids.

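### Minor safety-text conflict: the Appendix B hepatic footnote joins the liver limits with 'or', so read literally it allows a delay where Section 6.4 requires a permanent stop

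*Combined protocol and SAP*

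**What the plan says.** **Section 6.4** opens: "Treatment with combination nivolumab and ipilimumab must be permanently discontinued for the following". On the liver it says: "Any drug-related liver function test (LFT) abnormality that meets the following criteria requires discontinuation". It then lists three criteria, any one of which is enough:

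- AST or ALT above 8 x ULN;
- total bilirubin above 5 x ULN;
- AST or ALT above 3 x ULN at the same time as total bilirubin above 2 x ULN.

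**Appendix B**, the algorithms for nivolumab, has this footnote on the hepatic page: "I-O therapy may be delayed rather than discontinued if AST/ALT ≤ 8 x ULN or T.bili ≤ 5 x ULN".

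**Appendix C**, the algorithms for ipilimumab, has a parallel footnote. It begins "Ipilimumab may be held/delayed rather than discontinued if AST/ALT" and goes on to require AST/ALT no higher than 8 x ULN *and* bilirubin no higher than 5 x ULN. It makes restarting ipilimumab subject to the protocol's retreatment criteria.

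**How Section 6.4 reaches nivolumab alone.** The lead sentence names only the combination. Section 5.7 makes continued dosing in both cohorts, including Cohort 2 maintenance, conditional on Section 6.4. Section 5.10 lists "Unacceptable adverse event/toxicity as specified in Section 6.4" as a reason to stop and adds "Participants will be removed from the protocol therapy when any of these criteria apply".

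**Standing of the algorithms.** Section 6.1.1 recommends them as guidance that complements medical judgment. Appendix B adds: "Where applicable the Approved Label should be used for guidance around dose modifications and discontinuation". No sentence says which text prevails if a footnote and Section 6.4 disagree.

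**The concern.** The two appendices use the same two limits but join them differently, and only the 'and' version fits Section 6.4 on those limits. A clinician managing hepatotoxicity is likely to have the algorithm page open. For a patient on nivolumab alone, Appendix B is the only hepatic algorithm that applies, so no second page corrects the 'or'. That patient could be held and later restarted where the protocol requires a permanent stop.

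The patients concerned are those still on drug in Cohort 1 and those in Cohort 2 who have reached nivolumab maintenance.

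The criterion absent from the wording of both footnotes also matters. Its laboratory thresholds are those in the protocol's own definition of potential drug-induced liver injury (Section 7.2.8). An event meeting that full definition, which also requires no initial cholestasis and no other apparent cause, must be reported as an SAE.

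**Working it through.** The plan states no figure to reproduce here. The check compares the rules as logical conditions. Let A be AST or ALT and B be total bilirubin, both in multiples of ULN, for a drug-related abnormality.

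- Section 6.4, stop: (A > 8) or (B > 5) or (A > 3 and B > 2)
- Appendix B read literally, delay allowed: (A ≤ 8) or (B ≤ 5)
- Limits joined by 'and', delay allowed: (A ≤ 8) and (B ≤ 5). This is the Appendix C wording. It is also what Appendix B means if its 'or' was intended as 'whichever value is raised must be within its limit'.
- Corrected footnote, delay allowed: (A ≤ 8) and (B ≤ 5) and not (A > 3 and B > 2)

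| A | B | Section 6.4 | Appendix B, literal 'or' | Limits joined by 'and' | Corrected footnote |
|---|---|---|---|---|---|
| 12 | 1 | stop | delay allowed | no | no |
| 2 | 6 | stop | delay allowed | no | no |
| 9 | 6 | stop | no | no | no |
| 6 | 3 | stop (concurrent) | delay allowed | delay allowed | no |
| 4 | 2.5 | stop (concurrent) | delay allowed | delay allowed | no |
| 8 | 5 | stop (concurrent) | delay allowed | delay allowed | no |
| 6 | 1 | no stop | delay allowed | delay allowed | delay allowed |
| 2.5 | 4 | no stop | delay allowed | delay allowed | delay allowed |

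Three results follow.

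1. The literal 'or' is false only when A > 8 and B > 5 together. It therefore conflicts with Section 6.4 whenever just one limit is exceeded (rows 1 and 2).
2. Changing 'or' to 'and' removes those conflicts but leaves the region A above 3 up to 8 with B above 2 up to 5 (rows 4 to 6). Adding only the concurrent clause and keeping a literal 'or' leaves rows 1 and 2 in conflict. Both edits are needed for the footnote to agree with Section 6.4.
3. The corrected condition is the exact negation of the Section 6.4 condition. It leaves no conflict at any values, and it stops nobody whom Section 6.4 would not stop.

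The rows are test values chosen to show the logic. They say nothing about how often such values occur.

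**The case against.** The strongest reply is that the protocol already settles the matter. Section 6.4 is mandatory and lists all three criteria, Sections 5.7 and 5.10 carry it to both cohorts, and the footnote is permissive wording in a guidance appendix. The 'or' may be a drafting slip meant as 'whichever value is raised'. A single precedence sentence would then resolve every conflict.

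Most of this stands, and it is why the point is minor. A reader might infer that the protocol contains two competing discontinuation rules, or that Appendix B overrides Section 6.4. The documents do not support that: the body text is binding and the appendix is advisory. What remains is that no sentence states the precedence, the literal wording permits what Section 6.4 forbids, and the Section 6.4 lead sentence does not name the setting where Appendix B stands alone. A precedence sentence would settle the rule but leave misleading wording on the page used at the bedside.

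A second reply concerns the missing flowcharts. Both footnotes qualify boxes that are not shown, and a box might state the concurrent criterion or point to the protocol criteria. This stands. A reader might infer that the hepatic algorithms omit the criterion altogether; only the footnote wording can be shown to omit it. The 'or' against 'and' difference does not depend on the figures.

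A third reply is that Section 6.3 already calls for a permanent stop when both values are raised. It helps only in part. That bullet covers combined Grade 2 values, and the documents do not reproduce the CTCAE cut-offs, so it is not shown to cover AST 6 x ULN with bilirubin 3 x ULN.

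**Conclusion.** The conflict is real and minor. As written, the Appendix B footnote allows a delay when only one of the two limits is exceeded, and Section 6.4 does not. Confidence is high for the 'or' wording and lower for the omitted concurrent criterion, which depends on boxes that could not be checked. The conclusion assumes that Section 6.4 applies to nivolumab alone through Sections 5.7 and 5.10, and that it prevails over the appendices. The consequence is then possible misapplication at the point of care, mainly for nivolumab alone.

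Two further inferences should be resisted.

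- A reader might extend the conflict to combination dosing, or assume that the 'and' in Appendix C cancels the 'or' in Appendix B there. No sentence says how the two pages combine: one serves nivolumab and the other ipilimumab. Section 6.4 itself lets Cohort 2 patients resume nivolumab alone after full recovery from an event that ended the combination, so holding and restarting nivolumab there is not clearly a breach. No count is claimed for combination dosing.
- A reader might look for an effect on the efficacy result. PFS-6, the sample size, the error rates and the analysis are untouched.

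**What to change.** 1. In the Appendix B hepatic footnote, change 'or' to 'and'.
2. In Section 6.1.1, add: 'Where an algorithm and Section 6.4 differ, Section 6.4 governs.'
3. In the Section 6.4 lead sentence, name nivolumab monotherapy as well as the combination. This belongs in the core fix, because nivolumab alone is the main setting affected and now reaches Section 6.4 only by cross-reference.
4. Check the flowchart boxes. Unless they already state it, add to both hepatic footnotes: 'and not concurrent AST or ALT > 3 x ULN with total bilirubin > 2 x ULN'.

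The cost is amendment wording and the IRB approval that any amendment needs under Section 13.1. Nothing changes in the design, sample size, data collection or analysis.
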